Prior research evaluating dynamic cerebral autoregulation used thigh cuffs on healthy controls to artificially, but noninvasively and non-pharmacologically, induce brief changes in blood pressure. This study performed 6 episodes of 2 minute inflation in bilateral thigh cuffs to a pressure above the maximum systolic blood pressure of the awake, non-anesthetized subjects (Aaslid, Lindegaard et al. 1989). Other more recent studies have continued to use the thigh cuff technique in both healthy subjects (Tzeng, MacRae et al. 2014, Subudhi, Grajzel et al. 2015), as well as those with traumatic brain injury and stroke patients respectively (Bailey, Jones et al. 2013, Saeed, Panerai et al. 2013). Of these studies using thigh cuff in healthy controls, traumatic brain injury, and stroke patients, only one subject (1.2%) out of) 83 total (49 healthy controls, 12 traumatic brain injury, 22 stroke) withdrew due to discomfort from the thigh cuffs. None of these studies reported neurologic deterioration or any other adverse events secondary to thigh cuff utilization (Aaslid, Lindegaard et al. 1989, Bailey, Jones et al. 2013, Saeed, Panerai et al. 2013, Tzeng, MacRae et al. 2014, Subudhi, Grajzel et al. 2015).

Surgical literature supports the safety of pneumatic tourniquet devices for bloodless field techniques. For upper limb bloodless field surgery using a tourniquet device, two hours of cuff inflation is considered safe (Noordin, McEwen et al. 2009). Although no prospective trials have been conducted to identify the maximum safe duration of lower leg ischemia using a pneumatic tourniquet device, trials have been done to evaluate the difference in recovery with and without tourniquet use. One randomized controlled study demonstrated that for routine anterior cruciate ligament repair these devices are routinely used for a mean of 87 minutes with the cuff insufflated to an average of 269mmHg. This study was powered to determine if tourniquet use during surgery is associated with increased neuromuscular injury, strength deficits, or any impaired return of function. The study showed that there was no evidence of injury

Protocol Version dated March 17, 2016

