based on a wide range of tests (thigh girth, strength, functional testing, arthrometer evaluation, Lysholm knee scores and EMG) and 6-12 months (Arciero, Scoville et al. 1996). In previous experiments and in our proposed experiments, the thigh cuffs are inflated for only 2-3 minutes. This brief period of ischemia is nearly 30 times less than what has been previously studied in the surgical literature. Given the safety of prolonged thigh cuff inflation, the brief periods of arterial occlusion used in this study are expected to be safe and well tolerated.

The tourniquet system that will be used in this study has been approved by the FDA as a Class-I medical devices, indicating that they present minimal harm to the user and do not present a reasonable source of injury through normal use (Noordin, McEwen et al. 2009). Development in tourniquet systems over the past 30 years make use much safer, including increased cuff width, micro-computer monitoring systems, auto-shut off in event of power failure, battery backup, and audio-visual alarms. Increased cuff width results in lower required tourniquet pressure to stop blood flow (McEwen, Kelly et al. 2002) and should further improve tolerability of cuff inflation.

CHARACTERISTICS OF THE STUDY POPULATION

1. Target Population

Healthy adult volunteers with no history of prior brain ischemia.

2. Accrual

20 subjects provides 90% power to detect a moderate correlation (rho=0.6), with alpha=0.05, based on a single sided test of correlation using Pearson's correlation coefficient. Because of a combination of technical and individual factors, it may be that not all enrolled subjects provide analyzable data. The study will continue to enroll until we have complete, analyzable data on 20 subjects, or a maximum of 30 subjects will be enrolled. We will evaluate the quality of obtained data on a rolling basis and halt study enrollment as soon as we have met our goal of 20 subjects with data for analysis.

3. Key Inclusion Criteria

- A. Healthy Subjects
 - 1. Age \geq 18 years
- 4. Key Exclusion Criteria

A. Healthy Subjects

- 1. Pregnant women are excluded
- 2. Prisoners are excluded
- 3. Prior history of vascular risk factors (hypertension, diabetes, hyperlipidemia, coronary artery disease, atrial fibrillation, prior myocardial infarct or stroke, transient ischemic attack, or history of smoking)
- 4. Prior neurosurgical procedure or traumatic brain injury, including hemicraniectomy or other skull defect.

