After obtaining informed consent, all subjects will be placed supine with the head of bed flat. A non-invasive Finapres blood pressure probe will be placed on a finger to continuously record arterial blood pressure. Heart rate will be calculated by analyzing the frequency of pulsatile blood flow. After the patient is comfortable optical probes will be attached to the patient's forehead. The probes are embedded in foam pads that will be secured to each side of the forehead using a combination of medical adhesive tape and a padded Velcro strap. The pads will be placed at the temporal margin of the forehead, superior to the frontal sinuses. A transcranial Doppler ultrasound probe will be placed on the scalp at the temporal bone to insonate the middle cerebral artery (MCA) and/or the anterior cerebral artery (ACA) bilaterally and secured in place using a commercial head frame The goal will be to insonate the MCA on one side and the ACA in the contralateral side. Due to limitations of TCD insonation and variability in temporal bone windows, this may not be possible in all subjects. In this way, optical blood flow from the right and left frontal cortex and blood flow velocity in the anterior cerebral circulation will be recorded simultaneously during the study session. A large blood pressure cuff will be placed around each thigh. Both cuffs will be connected together with a large bore Y-adapter that is connected to a bulb inflator.

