Once the patient is comfortable, optical blood flow and TCD blood flow velocity will be measured for 5 minutes to establish a baseline. Both thigh cuffs will then be inflated to 20 mmHg above the patient's systolic blood pressure so that blood flow to the legs is occluded. Occlusion will be maintained for 4 minutes, followed by simultaneous deflation of bilateral cuffs and concurrent recording of blood pressure and CBF for an additional 4 minutes; 3 measures will be obtained per subject and averaged to establish a curve. The rapid deflation of the thigh cuffs will induce a 5-10% step decrease in blood pressure that is expected to last for about 10 seconds before cardiovascular reflexes restore MAP to baseline levels. During the thigh cuff deflation, changes in pulsatile blood pressure, and TCD blood flow velocity will be continuously recorded; oCBF will be recorded every 0.5 seconds. Intact autoregulation should cause a restoration of cerebral blood flow to pre-deflation values within 5-10 seconds in spite of the prolonged decrease in systemic blood pressure. We expect to see a sudden drop in optical cerebral blood flow and MCA velocity followed by a quick increase in both of these parameters. The change in cerebrovascular resistance (Δ CVR) can be calculated by dividing arterial blood pressure by cerebral blood flow. Δ CVR will be calculated using both optical CBF values and MCA velocity. The magnitude of Δ CVR over time gives a measure of dynamic cerebral autoregulation (see below for details regarding analysis). The thigh cuff occlusion will be repeated 4 times in each subject to establish a curve. A diagram of the study flow is shown below:

2. Data Collected

Information will be collected and stored securely from all study subjects. This information will include the following: age, sex, past medical history, current medications, non-prescription drug use.

3. Quantitative and Statistical Analysis

dCA will be calculated as change in blood pressure from baseline (Δ BP) divided by change in cerebral blood flow from baseline (Δ CBF) at each time point, thus dCA = Δ BP/ Δ CBF(Aaslid, Lindegaard et al. 1989); this data will be plotted against time in seconds.

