Risks of DCS/Optical Blood Flow Monitoring: There is a risk of damage to the eye if the eye is exposed directly to the infrared light coming from the DCS patches. Damage could include retinal (light sensitive tissue at the back of the eye) burn. In order to prevent such an injury we will put optical fibers in a foam pad where they will be away from the surface of the skin. Therefore the light will be concentrated on the top of the head. The probes will be secured by a lightly wrapped bandage which will ensure that the light pads remain secure, covered, and away from the eyes. In addition the patient can elect to wear safety goggles that will reduce the risk of retinal damage if probes and protective foam become dislodged.

A research staff member will be continuously monitoring the subject while on the study and will be able to cycle the light off in less than three seconds. The instrument has passed clinical engineering safety inspection.

A member of the study team will be present at all times and will assist in the placement of the probe(s) and the collection of the data. No discomfort should be associated with the procedure.

Risks of Transcranial Doppler Monitoring:

There is no known risk of the use of ultrasound equipment for transcranial doppler monitoring. It is non-ionizing radiation, and therefore does not have the same risk as x-rays or other types of radiation.

A member of the study team will be present at all times and will assist in the placement of the probe(s) and the collection of the data. At times the TCD probes can cause mild discomfort. If the subject feels uncomfortable study personnel will attempt to reposition the probes to maximize comfort. If at any point the discomfort becomes significant, the study will be terminated.

Risks of non-invasive blood pressure monitoring:

There is no known risk of the use of non-invasive blood pressure monitoring via the Finapress system.

A member of the study team will be present at all times and will assist in the placement of the probe and the collection of the data. No discomfort should be associated with the procedure.

Risks of Thigh Cuff Manipulation of Blood pressure

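### The safety text and Procedures disagree on occlusion time, repeat count, probe site and device description, so the stated ischemia ratio does not fit the planned procedure

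*Combined protocol and SAP*

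**What the plan says.** **Inflation time.** BACKGROUND, Thigh Cuff Utilization, states: "In previous experiments and in our proposed experiments, the thigh cuffs are inflated for only 2-3 minutes". The next sentence reads: "This brief period of ischemia is nearly 30 times less than what has been previously studied in the surgical literature". The lower-limb comparator in that section is a randomized trial in knee ligament repair, for which it says "these devices are routinely used for a mean of 87 minutes with the cuff insufflated to an average of 269mmHg". STUDY PROCEDURES, 1. Procedures, says: "Occlusion will be maintained for 4 minutes". RISK/BENEFIT ASSESSMENT, 1. Potential Study Risks, likens the cuff discomfort to an ordinary arm-cuff reading prolonged to 3 minutes.

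**Repeat count.** Procedures averages 3 measures per subject, and later in the same paragraph has the occlusion repeated 4 times. STUDY PROCEDURES, 3. Quantitative and Statistical Analysis, averages dRoR over 5 trials.

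**Probe site and fixation.** The optical-monitoring paragraph of Potential Study Risks says: "Therefore the light will be concentrated on the top of the head". It has the probes held by a bandage. Procedures says: "The pads will be placed at the temporal margin of the forehead, superior to the frontal sinuses". There they are held by tape and a Velcro strap. The Background section on optical measurement agrees with Procedures: frontal probes, tape and a Velcro band.

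**Device.** Thigh Cuff Utilization says: "The tourniquet system that will be used in this study has been approved by the FDA as a Class-I medical devices". Procedures puts a large blood pressure cuff on each thigh and adds: "Both cuffs will be connected together with a large bore Y-adapter that is connected to a bulb inflator". DRUGS OR DEVICES refers only to a thigh cuff device.

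**The concern.** Cuff occlusion is the study's main physical intervention, and laser light near the eye is the hazard named in the overall risk statement. On both, the text that argues for safety differs from the text that tells staff what to do. Three things are at stake.

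- A numerical safety statement, the factor of nearly 30, is more favourable than Procedures supports.
- The discomfort described in the risk section is for a shorter inflation than the one Procedures specifies.
- An operator or ethics reviewer who reads the whole document cannot tell which inflation time or how many inflations apply.

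**Working it through.** **Inputs**

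- Surgical comparator, thigh: mean 87 minutes (Thigh Cuff Utilization).
- Study inflation in the safety text: 2 to 3 minutes (Thigh Cuff Utilization); 3 minutes (Potential Study Risks).
- Study inflation in Procedures: 4 minutes.
- Number of occlusions: 3 or 4 (Procedures), 5 (Quantitative and Statistical Analysis).

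**Step 1: reproduce the plan's figure.** Ratio = surgical minutes / study minutes.

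- At 3 minutes: 87/3 = 29.0, which matches the stated factor of nearly 30.
- At 2 minutes: 87/2 = 43.5, which does not.

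So the figure is correct arithmetic for the 3-minute end of the range.

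**Step 2: use the time in Procedures.** 87/4 = 21.75, about 22 times shorter per inflation. The stated factor is not reproduced.

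**Step 3: context only, total occlusion at 4 minutes each.**

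| Occlusions | Total (min) | 87 / total |
|---|---|---|
| 3 | 3 × 4 = 12 | 7.25 |
| 4 | 4 × 4 = 16 | 5.4 |
| 5 | 5 × 4 = 20 | 4.35 |

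These totals add separate inflations with recovery between them, while the surgical figure is for tourniquet use in a single operation. They should not replace the per-inflation ratio. They do show that the unsettled count changes a subject's total exposure by 20 − 12 = 8 minutes. If repeated 4 times means four further occlusions after the first, the total is 5 and agrees with the analysis section, but 3 still conflicts.

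**Step 4: set the non-numerical passages side by side.**

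| Item | Safety text | Procedures |
|---|---|---|
| Probe site | Top of the head | Temporal margin of the forehead |
| Probe fixation | Bandage | Tape and Velcro strap |
| Cuff device | Tourniquet system | Blood pressure cuffs, Y-adapter, bulb inflator |

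The probe site is a direct conflict. The fixation wording differs. The device wording also differs, but the two descriptions could refer to the same equipment.

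**The case against.** The strongest reply is that the safety case does not depend on the disputed sentences, and much of that stands.

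- **Direct evidence.** Thigh Cuff Utilization cites thigh-cuff studies covering 83 subjects, with one withdrawal for discomfort and no reported adverse events. One of them used six 2-minute inflations, 6 × 2 = 12 minutes in all, which equals the total for three 4-minute occlusions. The surgical ratio is a secondary comparison. Even so, each inflation in Procedures is twice as long as in that study.
- **Eye safety.** Several safeguards do not depend on probe site: fibers set in foam, optional goggles, staff able to cut the light within three seconds, and institutional laser-safety approval. The sentence on the top of the head is still wrong for a forehead probe, but the argument does not fall with it.
- **Device.** The automatic shut-off, battery backup and alarms are listed as general advances in tourniquet systems, not as features of the study device. Nothing shows that the bulb-inflated cuff is not Class I. The point is therefore limited to inconsistent description.
- **Another route to 30.** The two hours cited for upper-limb tourniquets gives 120/4 = 30. That uses an arm figure for a thigh cuff and a 4-minute time that the Background does not state. It does not rescue the sentence, which directly follows the one giving 2 to 3 minutes.

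Two stronger readings are tempting. A reader might infer that the rating of a minor increase over minimal risk is unsupported. The documents do not show this: the paragraph giving that rating discusses retinal exposure and benefit to others, and cites neither the ratio nor the cuff device. A reader might also infer that the inflation device distorts the pressure step used in dRoR. No section links device type to the steadiness of occlusion or the speed of release, and blood pressure is recorded continuously through deflation.

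**Conclusion.** The point holds as an internal contradiction in the safety description. The stated factor of nearly 30 fits a 3-minute inflation; at the 4 minutes in Procedures it is 21.75. The discomfort text is for 3 minutes against 4. The repeat count has three values, and the probe site in the eye-risk paragraph conflicts with the two sections that describe placement. The device wording is a lesser matter of consistency.

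The ratio rests on 87 minutes being the intended surgical comparator, which is the only one given for the thigh. A single inflation of 4 minutes, and every total up to 20 minutes, remains well below 87 minutes. This is a misdescribed safety case, not evidence that the procedure is unsafe. It should be corrected, but it does not overturn the overall risk rating and has no demonstrated effect on the dRoR analysis.

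**What to change.** 1. Reconcile Thigh Cuff Utilization, Procedures, Quantitative and Statistical Analysis, and the thigh cuff paragraph of Potential Study Risks to one occlusion time and one repeat count. Restate the surgical ratio and the discomfort description for that time. If total occlusion is mentioned, label it as context.
2. Reconcile the optical-monitoring paragraph of Potential Study Risks with Procedures and the Background section on optical measurement, so that one probe site and one method of fixation appear throughout.
3. Use one device description in Thigh Cuff Utilization, DRUGS OR DEVICES and Procedures, and cite only the features that this device has.

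No position is taken here on which time, count, site or device is right; that is for the investigators. The cost is a protocol wording amendment. If the time settled on is longer than 3 minutes, the stated ratio becomes less favourable.

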Non-Invasive Measurement of Dynamic Autoregulation of Cerebral Blood Flow Using Diffuse Correlation Spectroscopy

Principal Investigator:	[name], MSCE [name] [contact]
	[contact]
IRB Number:	821705
NCT number:	NCT02442856
Date:	March 17, 2016

Application for Review of Human Research: IRB Protocol Summary Biomedical Research

Section II

Principal Investigator: [name], MSCE [name] [contact]

PROTOCOL # 821705

Date: March 17, 2016

PROTOCOL TITLE

1. *Full Title:* Non-Invasive Measurement of Dynamic Autoregulation of Cerebral Blood Flow Using Diffuse Correlation Spectroscopy

2. Brief Title: Non-invasive Measurement of Cerebral Dynamic Autoregulation

STUDY SPONSORSHIP

1. Funding Sponsor: NIH R25 Research Grant

PROTOCOL ABSTRACT

List of Abbreviations

OBJECTIVES

1. Overall Objectives

The overall objective of this study is to evaluate the use of diffuse correlation spectroscopy (DCS) to non-invasively measure dynamic cerebral autoregulation (dCA). Cerebral autoregulation (CA) refers to the process by which cerebral blood vessels change their caliber to ensure constant cerebral blood flow (CBF) in the face of changes in cerebral perfusion pressure (CPP). Optical cerebral blood flow (oCBF) measurements will be correlated with changes in arterial blood pressure (ABP) to assess how CBF is maintained in response to changes in ABP. CA measured by DCS will be compared with reference measurements using Transcranial Doppler (TCD).

2. Primary Objective

The primary objective of this study is to validate the use of DCS to quantify dCA in healthy controls. We will measure dCA with both TCD and DCS during acute changes in mean arterial pressure using thigh cuff deflation techniques in healthy subjects. Measurements will be compared between TCD and DCS in order to validate DCS as a tool to measure dCA. We hypothesize that DCS based measurements will be tightly correlated to TCD based measurements. We hypothesize that continuous oCBF measurements will allow calculation of an autoregulation index that will correlate well with established methods for measuring CA using TCD. The primary measured variable will be relative change in cerebral blood flow using DCS.

BACKGROUND

Cerebral Autoregulation

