Prior human studies have documented that CA tightly controls flow over a range of mean arterial pressure from 60-150mmHg (Paulson, Strandgaard et al. 1990). However, recent studies suggest that autoregulation may be impaired for up to 2 weeks following acute ischemic stroke (AIS), and that CA impairment may lead to poorer outcomes (Dawson, Blake et al. 2000, Dawson, Panerai et al. 2003, Reinhard, Roth et al. 2005, Atkins, Brodie et al. 2010, Aoi, Hu et al. 2012, Reinhard, Rutsch et al. 2012). The extent of CA impairment in acute stroke is likely highly variable. Early human studies determined that CA is impacted by age-related diseases, including hypertension and diabetes (McHenry, West et al. 1974, Dawson, Blake et al. 2000, Aries, Elting et al. 2010). Animal models have also demonstrated impaired dCA in AIS and that the tissue becomes much more vulnerable to changes in blood pressure (Yang, Shah et al. , Smeda, VanVliet et al. 1999, Smeda 2003). Based on the principle that CA is impaired following an acute ischemic event, current treatment recommendations revolve around tactics that increase cerebral perfusion (Goldstein 2000, Dawson, Panerai et al. 2003). The American Heart Association/American Stroke Association guidelines recommend permissive hypertension to systolic of 220mmHg and diastolic to 120mmHg (Adams, del Zoppo et al. 2007). However, above the upper limit of CA blood vessels are

not able to adequately constrict to limit blood flow, which can lead to endothelial injury, breakdown of the bloodbrain barrier, and potentially cerebral edema (Nazir, Overell et al. 2004, Nazir, Overell et al. 2005). Data derived from this project will provide the groundwork for future projects using the DCS technique which may be able to establish a new bedside mechanism for identifying patients in whom dCA is impaired, allowing for more individualized use of permissive hypertension, intravenous fluids, and vasopressors.

Limitations of existing autoregulation measurements

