The data recorded from the TCD monitoring will be used to quantify the relation between changes in cerebrovascular resistance (Δ CVR) and blood pressure (Δ BP) as calculated by ROR = (Δ CVR/ Δ T)/ Δ BP and will be plotted along a curve for the first few seconds after cuff deflation (Aaslid, Lindegaard et al. 1989, Tiecks, Lam et al. 1995, Panerai, White et al. 1998, Lang, Mehdorn et al. 2002). The purpose of collecting TCD data is to show a correlation between the ROR calculated from TCD measures to that of dCA via DCS measurement, further validating our DCS measurements.

The optical CBF output is directly recorded as relative CBF. For blood flow velocity measured by TCD, relative CBF can be approximated by normalizing flow to baseline. This is an approximation of CBF that assumes that the vessel diameter does not change over time. Once the relative change in CVR over time is calculated, a dynamic rate of regulation index (dRoR) can be calculated by dividing the slope of the CVR over time curve by the maximum change in blood pressure (i.e. (Δ CVR/ Δ t)/ Δ BP). Intuitively, if autoregulation is intact, there should be a steep decrease in cerebrovascular resistance with a drop in blood pressure. Perfect autoregulation would result in dRoR = 1.

Baseline heart rate, MAP, and MCA velocity will be recorded for each subject and descriptive statistics including mean and standard deviation will be reported for these values. For dRoR calculation, a mean dRoR will be calculated for each subject (from 5 trials) using both optical CBF and TCD. The optical dRoR and TCD dRoR will be compared for each subject and significant differences will be evaluated using Student's t-test or Wilcoxon rank-sum as appropriate. We will quantify the correlation between dRoR measured with TCD and DCS using Pearson or Spearman correlation coefficient as appropriate.

4. Confidentiality

How will confidentiality of data be maintained? Check all that apply.

- Paper-based records will be kept in a secure location and only be accessible to personnel involved in the study.
- Computer-based files will only be made available to personnel involved in the study through the use of access privileges and passwords.
- Prior to access to any study-related information, personnel will be required to sign statements agreeing to protect the security and confidentiality of identifiable information.
- Whenever feasible, identifiers will be removed from study-related information.

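### The plan to validate DCS against TCD estimates neither bias nor individual agreement in dRoR, and passing both planned tests is compatible with wide individual disagreement

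*Combined protocol and SAP*

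**What the plan says.** Objectives, 2. Primary Objective, gives the purpose: "Measurements will be compared between TCD and DCS in order to validate DCS as a tool to measure dCA". The hypothesis there is one of association: "We hypothesize that DCS based measurements will be tightly correlated to TCD based measurements".

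Study Procedures, 3. Quantitative and Statistical Analysis, defines dRoR as the slope of cerebrovascular resistance over time divided by the maximum change in blood pressure, with 1 meaning perfect autoregulation. A mean dRoR is formed per subject from the optical signal and from TCD. Two between-device analyses of it follow. The first is a test: "The optical dRoR and TCD dRoR will be compared for each subject and significant differences will be evaluated using" Student's t-test or a Wilcoxon rank-sum test. The second is an association measure: "We will quantify the correlation between dRoR measured with TCD and DCS using Pearson or Spearman correlation coefficient as appropriate".

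The sample size under Characteristics of the Study Population, 2. Accrual, is "20 subjects provides 90% power to detect a moderate correlation (rho=0.6), with alpha=0.05", "based on a single sided test of correlation using Pearson's correlation coefficient".

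No section plans a mean difference with a confidence interval, limits of agreement, a concordance or intraclass coefficient, or a numerical criterion for validation.

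**The concern.** Both devices yield dRoR by the same formula on a scale whose absolute value has meaning, so each subject supplies a directly comparable pair. The natural validation question is how far apart the two values in a pair lie, on average and for an individual. The plan does not estimate either. A correlation is unchanged by a constant shift or a rescaling of one device. A difference test addresses only whether the means differ, and its result depends on scatter as well as on bias.

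At stake is what a reader can conclude. The study could report that DCS and TCD are correlated and not significantly different, and give no figure for the spread of individual differences. The Background looks ahead to bedside identification of patients with impaired autoregulation, "allowing for more individualized use of permissive hypertension, intravenous fluids, and vasopressors". That is offered as groundwork for future projects, but individual scatter is the property on which such later work would depend.

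**Working it through.** **Inputs from the protocol (Accrual).** 20 analysable subjects, rho = 0.6, alpha = 0.05 one-sided, stated power 90%. Enrolment is built around that number: "The study will continue to enroll until we have complete, analyzable data on 20 subjects, or a maximum of 30 subjects will be enrolled".

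**Assumptions.** Normal data, one pair of dRoR means per subject, and a two-sided 5% paired t-test. Pairing is the reading more favourable to the plan, which does not say whether the t-test is paired and names rank-sum, a test for independent samples. The documents give no SD or CV for dRoR, so a CV range of 10% to 50% is shown.

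**1. The plan's own figure.** Fisher z: atanh(0.6) × √17 − 1.645 = 0.693 × 4.123 − 1.645 = 1.213, giving power 88.7%. The bias-corrected form gives 89.9% and simulation of the exact test 90.3%. The stated 90% is reproduced. The smallest significant r is 1.734 / √(18 + 1.734²) = 0.378.

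**2. Limits of agreement at rho = 0.6, no bias.**
- Equal device SDs: SD of differences = SD × √(2(1 − 0.6)) = 0.894 SD; half-width 1.96 × 0.894 = 1.75 SD.
- All extra noise in DCS: noise SD = SD × √(1/0.36 − 1) = 1.333 SD; half-width 1.96 × 1.333 = 2.61 SD.

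As a percentage of mean dRoR:

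| Assumed CV | Equal SDs | All extra noise in DCS |
|---|---|---|
| 10% | ±18% | ±26% |
| 20% | ±35% | ±52% |
| 30% | ±53% | ±78% |
| 50% | ±88% | ±131% |

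The limits reach 50% only from a CV of about 29% (0.50 / 1.75) or 19% (0.50 / 2.61).

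**3. Chance of passing both tests with no bias.** Passing means r > 0.378 and a non-significant paired difference. Simulation at n = 20 and rho = 0.6 gives 85% to 86%, whatever the CV. This is close to 0.95 × 0.90 = 0.86. With an unpaired t-test it is about 90%.

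**4. Chance of passing both tests with bias (CV 30%).**
- DCS reading half of TCD: 0.01% or less for r between 0.4 and 0.8.
- DCS reading 20% low (proportional error), r = 0.6: about 6% with equal device CVs and about 22% with all extra noise in DCS. These are two noise models, not bounds; other forms of bias give other figures.
- With equal SDs and rho = 0.6, the paired test has 80% power for a mean difference of 0.59 SD. At CV 30% that is 0.59 × 30% = 18% of the mean.

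**5. Precision of an agreement analysis at n = 20.** In SDs of the differences, the 95% CI half-width is 2.093 / √20 = 0.47 for the mean difference. For each limit it is 2.093 × √(1/20 + 1.96²/38) = 0.81.

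**The case against.** The strongest reply is that the study declares correlation as its hypothesis, sizes itself on correlation, and collects TCD data to show one. On that view the difference test is secondary. A reader might infer that a non-significant difference is to be read as agreement, but no section says so. That part of the reply stands.

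Several other points also stand:

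- With no bias, a non-significant mean difference is the correct result, so the 85% does not count errors. It shows only that this outcome carries no information about scatter.
- It is tempting to say that the two tests together reward a noisy device. Noise also lowers r: with no bias, the joint pass rate falls from 95% at r = 0.8 to 85% at 0.6 and 53% at 0.4.
- A reader might infer that DCS could be wrong by a large factor and still pass. The correlation would miss this, but at CV 30% the difference test would not.
- A flat statement that readings may differ by more than 50% needs a CV that the documents do not supply.
- Disagreement is not the same as DCS error. The protocol itself says that TCD measures velocity and only approximates flow.
- The study enrols healthy volunteers and does not claim to support individual treatment decisions now.

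None of this supplies the missing estimate. The objective speaks of validating DCS to quantify autoregulation, and association alone does not establish that. The plan already compares levels as well as association, but with a test that cannot show agreement.

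**Conclusion.** The point holds as a gap in the analysis plan: followed exactly, it yields no estimate of bias with its uncertainty and none of individual disagreement. The gap concerns individual scatter and modest bias, not gross scale error. At the design correlation, limits of ±1.75 between-subject SDs (equal SDs, no bias) would sit behind a pass on both tests in about 85% of trials. Any percentage is conditional on the unstated CV and on which device carries the noise. The stated power is not in error, and the documents do not support reading the plan as an equivalence claim based on non-significance. The change is worth making because it answers the stated objective at almost no cost.

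**What to change.** In Study Procedures, 3. Quantitative and Statistical Analysis, keep the correlation as the measure of association and add, from the same per-subject pairs:

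1. the mean DCS-minus-TCD difference in dRoR with its 95% CI;
2. Bland-Altman 95% limits of agreement with CIs, on the log or ratio scale if the spread grows with the mean.

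State that a non-significant difference test will not be taken as evidence of agreement. Report the limits as estimates, without a pass/fail margin: the documents offer no basis for one, and 20 pairs locate each limit only loosely. Interpret the limits as disagreement between two devices, not as error in DCS alone.

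The cost is a few lines of text and one plot, with no new subjects or measurements. The downside is that a good r may have to be reported beside wide limits that are themselves imprecise. For example, with equal SDs, rho = 0.6 and CV 30%, the SD of the differences is 0.894 × 30% = 27% of the mean, so each limit carries a CI of about ±0.81 × 27% = ±22 percentage points.
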